To attain a more comprehensive understanding of the patient's medication, the research coordinator may need to access the electronic health record (EPIC). EPIC can be used to confirm a patient's medications during the phone screen.

Observation Arm

For the observation arm, patients undergoing any eligible elective surgery at Stanford will be considered for inclusion (See *MAP-Pain Observation Eligible Procedures*).

MAP-Pain Standard Operating Procedures

Patients will be recruited via methods described above. After completion of the phone or email eligibility screening, the research coordinator will contact all participants to obtain full electronic consent for continued study participation.

Intervention Arm

For the intervention arm, the following operations will be considered for inclusion. These are chosen for the appropriateness of the intervention in the context of the surgery, and the willingness of the surgeon to refer eligible patients.

Total Knee Replacement

Total Hip Replacement

Patients will be recruited via methods described above. Initial screening will take place via a brief online eligibility survey, or with an approved phone screen either on the phone or via an in-person interview during the patient's pre-operative appointment. Patients will first be given a description of the study as per the approved phone screen to assess interest and answer any questions (see *Screening Questions* document). Eligibility will be determined by the research coordinator and/or PI, who will input responses to screening questions into REDCap or complete an eligibility checklist at the time of screening (see *Eligibility Checklist* document). Eligibility to continue into the intervention randomization will be confirmed at 2-weeks post-surgery. Patients who do not meet the criteria at this time-point will continue in the observational arm.

Patient Eligibility and Enrollment

Eligible and interested patients:

Priority consent is the Intervention; observational consent is offered secondarily when a patient is ineligible or not interested in the Intervention.

Written Informed consent may be obtained electronically, through completing of the "Electronic Consent" instrument through REDCap.

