During the pre-surgery call, the coordinator will schedule the post-surgical call fourteen days after the participant’s date of surgery. Unless a specific timeslot is requested by the participant, Post-Surgery calls should be scheduled in the REDCap Calendar at 23:45 for observation participants, and 23:59 for intervention Participants.

Post-Surgical Call

Fourteen days after the participant’s date of surgery, the study coordinator will call the participant to confirm their date of surgery, the date and time they were discharged from the hospital, and verify if the participant has been prescribed and is still using opioid medications for surgical pain. The coordinator will call the patient five times, or until the patient picks up. If possible and necessary, the coordinator should leave a voicemail and specify the name of the patient, the purpose of the call, and leave a return name and number. If appropriate, the coordinator will randomize the study participant immediately after their call.

Randomization

During the Post-Surgical Call (Fourteen days after surgery) the research coordinator should verify whether or not the intervention participant in question has been prescribed and is still using opioid medications for surgical pain. Those who meet this criteria will be randomized to either the Motivational Interviewing and Guided Opioid Weaning intervention, or Enhanced Usual Care. Those who do not meet this criteria will be placed in the Observational arm of the study.

Participants are randomized in the Transfer to Longitudinal Instrument in the MAP-Pain Enrollment REDCap. Upon clicking the “Randomize” button, the coordinator will be prompted to select the surgery type (THR/TKR) and confirm the randomization. The participant will be randomized to “1” or “0”, denoting MI+GOW and EUC respectively. Once randomized, the participant cannot be moved to a different study group, so care must be taken to ensure participant is randomized correctly.

MAP-Pain Standard Operating Procedures

After random group assignment, the Transfer to Longitudinal instrument must be saved to transfer the participant's group assignment to the MAP-Pain: Longitudinal Observation REDCap project. The coordinator will send an email to the appropriate NP, to inform them of a newly randomized participant, and set up an appointment for MI+GOW or EUC sessions to begin.

Blinding and Randomization Methodology

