Randomization table was pre-generated using SAS. Randomization occurs using blocked, stratified randomization by operation. Randomization table was pre-generated onto spreadsheets, with rows hidden (in Excel). Each randomized patient will receive the next available row (unhidden by the coordinator at 14 days post-surgery for randomization as needed).

The PI will be blind to the patient's randomization status until completion of analyses. Due to the limitations of REDCap's randomization module, the research coordinator cannot be blinded to the randomization status of the participant.

Enhanced Usual Care (EUC)

Participants will receive phone calls matching the duration and frequency of MI+GOW calls. [name], NP will contact participants via phone to review one topic per call in this sequence: 1) standardized instructions on taking opioid medications after surgery, 2) avoiding medication mistakes, 3) alternative methods for pain management after orthopedic surgery, 4) understanding complementary and alternative medicine, 5) safe opioid use, 6) local mental health resources (including a suicide prevention hotline), 7) prescription drug abuse. She will briefly review patient education brochures in a didactic style without a tailored discussion. She will remind participants to complete REDCap assessments.

Intervention

The experimental intervention arm is Motivational Interviewing and Guided Opioid Weaning (MI+GOW). A pain medicine nurse practitioner ([name], NP) will administer MI+GOW. See table below for MI Components. The GOW protocol will be a 25% total daily opioid dose reduction every 7 days with opioid discontinuation 7 days after reaching 1 opioid pill per day. During phone sessions, patients will be monitored for worsening pain and opioid withdrawal through administration of the NRS and SOWS with the protocol specified in the "Guided Opioid Weaning" table below. Participants will be reminded that they can always use less opioids than recommended. Non-adherence is opioid use greater than previously recommended via the last phone call. During the randomization call, the first MI appointment should be scheduled by referring to [name]'s schedule.

Table MI Components

Principles	Strategies	Information Recorded by Interventionist	Information and Advice Offered in an MI-consistent manner (Elicit patient's knowledge, Provide advice, Elicit feedback)
------------	------------	---	---

MAP-Pain Standard Operating Procedures

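### The Protocol gives two different assignment procedures, and the one in which the coordinator unhides spreadsheet rows does not assure allocation concealment

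*Protocol*

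**What the plan says.** **REDCap route** (Protocol, Randomization). The coordinator works in the Enrollment project and presses the Randomize button, after which "the coordinator will be prompted to select the surgery type (THR/TKR) and confirm the randomization". REDCap returns 1 (MI+GOW) or 0 (EUC), and the participant cannot afterwards change group.

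**Spreadsheet route** (Protocol, Blinding and Randomization Methodology). The list was generated in SAS, blocked and stratified by operation. Then: "Randomization table was pre-generated onto spreadsheets, with rows hidden (in Excel", and "Each randomized patient will receive the next available row (unhidden by the coordinator at 14 days post-surgery for randomization as needed". The next paragraph of that section nevertheless refers to REDCap's "randomization module, the research coordinator cannot be blinded to the randomization status of the participant".

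**The day-14 decision** (Protocol, Post-Surgical Call and Randomization). On the call the coordinator must "verify whether or not the intervention participant in question has been prescribed and is still using opioid medications for surgical pain". Assignment follows at once: "If appropriate, the coordinator will randomize the study participant immediately after their call". For a negative answer, "Those who do not meet this criteria will be placed in the Observational arm of the study"; the Screening section, under Intervention Arm, says the same: "Patients who do not meet the criteria at this time-point will continue in the observational arm".

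**Analysis** (SAP, Analytic Plan). The comparison is a log-rank test at two-sided 0.05. Cox regression adjusts for surgery type, and for other covariates only where baseline imbalance is seen.

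**The concern.** Allocation concealment means that whoever decides on entry cannot know the next assignment. Someone who can unhide one Excel row can unhide the one below it. The Protocol describes no password, sheet lock, independent custodian or access log for the spreadsheet.

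The person who would unhide the row is also the person who decides entry. That decision rests on a telephone report and on whether the opioid use is for surgical pain, so some judgement remains. A patient recorded as no longer using is never randomised, so intention-to-treat analysis cannot bring that patient back into the comparison.

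If entry decisions depended on a known next assignment, the arms could differ for reasons other than treatment. Adjusting for surgery type and observed baseline imbalance need not capture something unmeasured, such as how hard a patient seems to be finding it to stop at day 14.

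**Working it through.** **1. The two procedures side by side.** The plan states no figure on this point, so the core check is textual.

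| Item | Randomization | Blinding and Randomization Methodology |
|---|---|---|
| Tool | REDCap button | Excel list with hidden rows |
| Coordinator's action | Select THR or TKR, confirm | Unhide a row at day 14 |
| Future assignments visible? | Not described as visible | Protected only by hiding |
| Relation to the other route | Spreadsheet not mentioned | REDCap module mentioned, link not explained |

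Both texts describe an action by the coordinator at the moment of assignment. They cannot both be the operative procedure as written.

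**2. What steering could do to the primary test.** From the documents: 220 randomised and 10% censoring (Study Overview). Assumed:
- 1:1 allocation, so 110 per arm, and no true treatment effect;
- 40% of candidates are slow stoppers; exponential times with median 20, 12 or 8 weeks for slow stoppers and 4 weeks for the rest;
- steering in one direction only: a share *d* of still-using candidates facing an MI+GOW row is diverted, drawn from those predicted to be slow;
- sensitivity and specificity of that prediction both 100%, 80% or 70%.

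Number diverted = 110*d*/(1 − *d*). For *d* = 0.04, 0.08, 0.12 and 0.16 this is about 5, 10, 15 and 21 patients.

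Share of diverted patients who are truly slow: PPV = 0.4·sens / [0.4·sens + 0.6·(1 − spec)].
- 100%: 1.00
- 80%: 0.32/(0.32 + 0.12) = 0.73
- 70%: 0.28/(0.28 + 0.18) = 0.61

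Slow share left in MI+GOW = (0.4 − *d*·PPV)/(1 − *d*). At *d* = 0.16 this is 28.6%, 33.8% and 36.0% for 100%, 80% and 70% accuracy, against 40% in EUC.

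Simulated log-rank false positives favouring MI+GOW (nominal 2.5%), 20,000 replicates per setting, Monte Carlo standard error at most 0.3 points:

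| Prediction | Medians (weeks) | *d* = 4% | 8% | 12% | 16% |
|---|---|---|---|---|---|
| Perfect | 20 vs 4 | 4.0% | 6.6% | 10.8% | 17.6% |
| Perfect | 12 vs 4 | 3.7% | 5.6% | 8.3% | 12.5% |
| Perfect | 8 vs 4 | 3.4% | 4.8% | 6.1% | 8.0% |
| 80% | 20 vs 4 | 3.6% | 4.4% | 6.0% | 7.9% |
| 80% | 12 vs 4 | 3.1% | 4.0% | 4.7% | 6.2% |
| 80% | 8 vs 4 | 2.8% | 3.4% | 4.1% | 4.8% |
| 70% | 20 vs 4 | 3.1% | 3.7% | 4.3% | 5.5% |
| 70% | 12 vs 4 | 2.9% | 3.2% | 4.0% | 4.7% |
| 70% | 8 vs 4 | 2.9% | 3.1% | 3.6% | 4.1% |

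Without steering the simulation gives 2.3-2.7%. At 20 vs 4 weeks the apparent hazard ratio for cessation, with no true effect, is 1.03 to 1.16 under perfect prediction, up to 1.08 at 80% and up to 1.05 at 70%. Stopping follow-up at 50 weeks changes the rates by at most 0.5 points.

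**3. Could steering be detected afterwards?** Suppose day-14 negative decisions are counted against the arm of the next list row until 110 rows per arm are filled. Each candidate fills a row with probability *p*(1 − *d*) for MI+GOW rows and *p* for EUC rows, where *p*, the share still using at day 14, is assumed to be 0.5 to 0.8. A two-sided 5% two-proportion test then has power of about 14-25% at *d* = 8% and 42-71% at *d* = 16%.

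**4. What remains under REDCap alone.** With 1:1 permuted blocks of a fixed size *b* known to an unblinded coordinator, the share of assignments known with certainty is 1/(*b*/2 + 1): 50%, 33%, 25% and 20% for *b* = 2, 4, 6 and 8. The documents state neither block size nor ratio.

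**The case against.** The strongest reply is that REDCap is probably the working route. The Randomization section gives complete operating steps, and blaming REDCap's module for the coordinator's unblinding makes sense only if REDCap makes the assignment. The spreadsheet may have been the source of the uploaded list, or the wording may be left over. If so, this is mostly a documentation error. That reading is plausible, but the text does not state it, and a coordinator unhiding a row at day 14 is not an upload step. The document is a set of operating procedures given to all team members, last updated 10/15/2020, so leftover wording would still need removing.

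Second, steering would mean recording that a patient had stopped when the patient had not. Online opioid reports begin seven days after surgery and continue in the observational arm, which gives a partial cross-check. This limits discretion and makes heavy diversion less likely. It does not conceal the list.

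Third, every steering input is assumed and only one direction is modelled. A coordinator who wanted difficult cases to receive MI+GOW would bias the result against it. With imperfect prediction at 8 vs 4 weeks the rates are only 2.8% to 4.8%. This stands: the figures show what could happen, not what did. The textual conflict does not depend on them.

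**Conclusion.** The concern holds. The two sections describe different assignment procedures and nothing reconciles them. If the spreadsheet procedure is followed as written, concealment is not assured, because the coordinator who applies the day-14 criterion could know the next assignment first.

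Confidence is high on the conflict and on this conditional consequence. Whether concealment was in fact compromised cannot be judged from the documents. Under the stated assumptions the harm ranges from negligible (rare or inaccurate steering, or little difference in prognosis) through about 3-8% with imperfect prediction, to 17.6% only with perfect prediction, a fivefold contrast in medians and about 21 diversions. This should be corrected, but it is not evidence that the result is biased.

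**What to change.** - Reconcile the two sections: delete the row-unhiding procedure and keep only REDCap assignment. If the SAS list was loaded into REDCap, say so.
- Give enrolling coordinators no access to the list or spreadsheet. Keeping block sizes from them as well is a useful addition, since an unblinded coordinator who knows a fixed block size can foresee some assignments even under REDCap.
- Record and save the day-14 eligibility answer before an assignment is requested.
- State which route was used for patients already randomised, so that correcting the text does not obscure what was done. If some but not all were assigned from the spreadsheet, repeat the primary analysis without them as a sensitivity analysis.
- If day-14 decisions were kept in time order, tabulate negative decisions by the next list row within each surgery stratum. Given the power shown above, a clean table would not exclude modest steering. Comparison with the weekly questionnaires is supportive only, because they may also count opioid use for reasons other than surgical pain.

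The cost is one corrected paragraph, a change in file access and a little extra analysis. The retrospective table is possible only if time-ordered decisions were kept, which the documents do not say.

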The first session will be scheduled by the research coordinator; subsequent appointments will be made directly between the NP's and the patient. The first session must be scheduled between 14 and 21 days after the participant's date of surgery. After the initial call, NP's will be responsible for tracking and competing intervention calls.

Intervention Protocol

Participants randomized to MI+GOW will receive the intervention from a single provider ([name]). Of note, participants will have all opioids and additional pain medications prescribed by their surgeon during the study. [name] will only be providing advice regarding participants' opioid medications. Content of the MI call is detailed in the Intervention section above. Treatment engagement is defined as participation in >50% of phone sessions. Treatment initiation is defined as participation in at least 1 phone session.

Longitudinal Follow-up

Scheduling Follow-Up Assessments

Electronic surveys will be sent out automatically based on confirmed dates of surgery. Distribution of online assessments will occur via the REDCap survey invitations calendar defined in the Longitudinal Observation Project, beginning seven days after the date of surgery. A patient's official date of surgery will be entered into the "Pre-Surgery Call" instrument in REDCap during the Pre-Surgery call, and confirmed during the Post-Surgery call. The study team member may verify the date of surgery and time of discharge in EPIC and record it on the "Post-Surgery Call" instrument.

Medical Chart Review

Research team member will review the patient's medical record for information required on the case report form.

Compliance Monitoring

Participant compliance with follow-up assessments will be assessed weekly through an automated reporting dashboard. Patients failing to complete two consecutive follow-up assessments be contacted

MAP-Pain Standard Operating Procedures

by the research coordinator, to encourage continued participation. The coordinator may offer to limit the participant's follow-up to monthly surveys, to maintain follow-up data collection for the participant.

Survey Frequency Reduction

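### The unblinded coordinator decides day-14 eligibility and then randomises from a blocked list, so the next assignment may be guessed better than chance at a step that intention-to-treat analysis cannot repair

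*Protocol*

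**What the plan says.** The Protocol gives one role every step at the point of entry to the randomised comparison.

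- **Eligibility.** On the day-14 call (Randomization section), "the research coordinator should verify whether or not the intervention participant in question has been prescribed and is still using opioid medications for surgical pain". Patients judged not to qualify go to the observational arm and are not randomised.
- **Randomisation.** Under Post-Surgical Call: "If appropriate, the coordinator will randomize the study participant immediately after their call". In the module, "the coordinator will be prompted to select the surgery type (THR/TKR) and confirm the randomization". The result appears as 1 or 0. The coordinator then saves the form that carries the assignment into the follow-up project and emails the nurse practitioner.
- **The list.** Under Blinding and Randomization Methodology: "Randomization occurs using blocked, stratified randomization by operation". Block size, fixed or varying blocks and allocation ratio are not given. The same section says the table was also placed on a spreadsheet with hidden rows that the coordinator unhides.
- **Blinding.** "Due to the limitations of REDCap's randomization module, the research coordinator cannot be blinded to the randomization status of the participant". The PI stays blind, but does not make the day-14 call.
- **After assignment.** Under Schedule: "The first session will be scheduled by the research coordinator; subsequent appointments will be made directly between the NP's and the patient". The Intervention section has the first MI appointment arranged during the randomisation call.

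These sections require no locking of the eligibility answer before randomisation and no second person to confirm it.

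**The concern.** In a blocked list, past assignments within a stratum carry information about the next one. Someone who knows them and also decides who enters can, without intending to, let the expected arm colour a doubtful eligibility call. This remains even if assignments come only from the REDCap module and no future row is ever seen.

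The day-14 criterion has no stated look-back period or minimum use, so some patients who have nearly stopped may be open to judgement. They are plausibly the ones closest to the primary event, a return to baseline dose or lower. If more of them are diverted when one arm is expected, the arms differ in prognosis at entry. The SAP's intention-to-treat population contains only randomised patients with follow-up data, so it cannot recover anyone diverted before randomisation.

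**Working it through.** **Inputs.** From the Protocol: blocked list, operation as the only named stratum, two arms, intervention-arm goal 220 with 10% censoring. From the SAP: log-rank test, two-sided 0.05. Assumed: 1:1 ratio, fixed blocks of 2 to 8, 220 taken as the number randomised, and one coordinator or shared records.

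**Plan's own figure.** The plan gives no predictability figure. The only nearby design number is 220, and 198/0.90 = 220, so the goal fits 198 uncensored patients. No hazard ratio or power is stated from which to derive it.

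**Step 1: guessing from counts.** The guesser names the arm with fewer patients so far in the stratum and tosses a coin if tied. This does not need the block size. For a block of 2m:

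G = 1/2 + [4^m / C(2m, m) − 1] / (4m)

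For m = 2: 1/2 + (16/6 − 1)/8 = 0.708. Listing confirms it: AABB gives 2.5 correct guesses, ABAB 3 and ABBA 3, and the mirror images give the same, so the mean is 8.5/3 = 2.83 of 4.

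**Step 2: certainty.** If the block size is known, an assignment is certain once one arm's places in the block are used up. The expected share is 1/(m + 1).

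| Block | Correct guess | Correct when counts differ | Certain in advance | Of 220 |
|---|---|---|---|---|
| 2 | 75.0% | 100% | 1/2 | 110 |
| 4 | 70.8% | 86% | 1/3 | 73 |
| 6 | 68.3% | 79% | 1/4 | 55 |
| 8 | 66.6% | 75% | 1/5 | 44 |

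With concealed assignments the values are 50% and 0.

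**Step 3: imbalance under full steering, block 4.** Suppose 30% of candidates are borderline and all of them are sent to observation whenever EUC is the likelier next arm. Counts differ for 58.3% of places. EUC is the likelier arm in half of these (29.2%) and is then correct 85.7% of the time. Those places supply 0.292 × 0.857 = 0.25 of all assignments to EUC and 0.292 × 0.143 = 0.042 to MI+GOW. Each arm holds 0.50, so the borderline share is 0.30 × (1 − 0.25/0.50) = 15% in EUC and 0.30 × (1 − 0.042/0.50) = 27% in MI+GOW.

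**Step 4: effect on the test.** Null simulations used 220 patients, two strata and the log-rank test, with 2,000 to 2,500 trials per setting. Borderline patients had 2 or 3 times the cessation hazard.

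- Full steering, 30% borderline, block 4: 7.5% to 8.3% (hazard ratio 2) and 11.2% to 11.3% (hazard ratio 3).
- Full steering, 30% borderline, block 6: 7.2% to 7.8% and 9.2% to 9.7%.
- Full steering, hazard ratio 2, smaller borderline group: 6.2% to 6.5% at 20%, and 5.9% at 10%.
- Half steering, 30%, hazard ratio 3, block 4: 4.7%, 6.0% and 7.1% in three separate runs.
- Quarter steering, hazard ratio 3: 4.8%. No steering: 4.9%.

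The standard error near 5% with 2,500 trials is √(0.05 × 0.95/2500) = 0.4 percentage points. The half-steering runs therefore differ by more than chance and should be read only as roughly 5% to 7%.

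**The case against.** Several points on the other side are fair.

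- **Blinding is not concealment.** The quoted sentence concerns patients already randomised and says nothing about foreseeing the next one. That is correct. The weakness comes from combining that sentence with a blocked list and with the same role judging eligibility.
- **A reader might infer that the coordinator always knows the next arm.** The documents do not support this. Certainty applies to a share of patients and needs a known block size; the rest is guessing. Omitting the block size from a protocol is not a fault. The Research Staff section names a lead coordinator, so there may be several, and no single one need see every assignment.
- **The criterion is fairly concrete.** On its face, an occasional pill for surgical pain counts as still using. The borderline group may be far below 30%, and then the effect is small. Patients' own weekly opioid reports, from day 7, could also expose steering, although no such check is planned at day 14.
- **Full steering is extreme.** It means rejecting every borderline patient on cue, which is closer to deliberate subversion than to unconscious influence. The direction in favour of MI+GOW follows from the steering assumed.
- **The SAP examines baseline balance and may adjust.** That could pick up a gross imbalance in a measured covariate. The SAP does not name day-14 opioid use as one, and adjustment does not restore diverted patients.
- **The hidden-rows spreadsheet is the more direct concealment weakness.** That is so, and the two should be handled together. Securing the spreadsheet alone would leave guessing from past assignments untouched.

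**Conclusion.** The concern holds as a structural opportunity for selection. Given one coordinator or shared records and 1:1 fixed blocks of 8 to 2, the next arm can be guessed correctly about 67% to 75% of the time. It is certain for 20% to 50% of patients if the block size is known or worked out.

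A reader might go on to infer that selection occurs or that the trial's type I error is inflated. The documents show neither. The figures of about 7% to 11% (full steering of a 30% borderline group) and roughly 5% to 7% (half steering) rest on an assumed borderline share, hazard ratio and behaviour.

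Nor do the documents show that the stated REDCap limitation is wrong, since they do not describe user rights. They do show that the unblinding also depends on giving this role the button. The change is worth making because it is cheap and the bias, if it arose, could not be removed by the planned analysis.

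**What to change.** 1. The coordinator records and locks the day-14 eligibility answer and operation type before any randomisation step. The answer is compared with the patient's own weekly opioid report, and disagreements are logged.
2. An existing team member with no part in eligibility then randomises and saves the transfer of the assignment. The research manager is preferable to the treating nurse practitioner. The coordinator has no access to the allocation spreadsheet and, as far as the REDCap set-up allows, none to the group field in either project.
3. The nurse practitioner books the first session. Amend the Schedule section, the notification email in Randomization, and the Intervention wording that places the first MI booking in the randomisation call. Revise the statement that the coordinator cannot be blinded.
4. Optionally, reissue the remaining list with undisclosed varying block sizes. This removes most certainty, but someone who sees past assignments would still guess about 72% correctly (sizes 2/4), 69% (4/6) or 68% (4/6/8). Separating the roles is therefore the essential step.

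**Cost.** SOP edits, a change to database access and to the transfer step, and a short hand-off that the existing 14-to-21-day window for the first session can absorb. No added staff, visits or patients. How much of the group field can be hidden needs checking against the actual REDCap set-up. Because treatment is open, the coordinator may still learn some arms from patients, so the change reduces predictability but may not abolish it.
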